An estimated 2.0 million adolescents (10-19 years old) worldwide are HIV-infected, and 220,000 adolescents aged 15-19 years old were newly infected in 2014. The majority (62%) of newly infected adolescents were female[8]. Unfortunately, global estimates of adolescent HIV and ART coverage are lacking because individuals between 10-15 years of age are considered children and those >15 years of age are considered adults. This makes it difficult to derive estimates for the group of adolescents and young adults between 10-24 years of age. In Kenya, an estimated 140,000 adolescents are HIV-infected, however, data are scant regarding adolescent ART coverage[8]. In a recent programmatic analysis of 22,832 adolescents and young adults aged 10-24 receiving ART in Kenya, young adolescents (aged 10-14) had a significantly lower CD4 at enrollment into HIV care than youth aged 15-24[9]. However, 15-24 year old youth had 2-fold higher loss to follow-up than younger adolescents. In another study of global trends, adolescents aged 10-19 years were noted to have a 50% increase in HIV-related mortality between 2005-2012 compared to a 32% decrease in non-adolescents during this same period[10]. This may be due to long-term complications from perinatally acquired infection or to poor adherence or motivation to continue in care. It is also possible that poor transition between pediatric to adult HIV treatment programs may contribute to poor adolescent outcomes.

Effective transition of children with HIV to self-directed health care requires disclosure of their diagnosis, however, pediatric HIV disclosure remains a challenge

In order for children to assume their own care, there must be accurate, well-conducted, and timely disclosure of their HIV status. Informing a child of any chronic illness is challenging because of a child's developmental limitations or because caregivers desire to protect children from negative consequences[11]. The complexities of disclosure are amplified for pediatric HIV because rather than affecting only the child, HIV is often a family infection and includes concerns about stigma and transmissibility [12-14]. Caregivers and HCWs are tasked with informing HIV-infected children that they have a chronic, potentially life-threatening, highly stigmatized disease during a critical time in the child's or adolescent's physical and psychosocial development.

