Studies in African countries have noted low rates of disclosure ranging from 3-41%, including studies of older children and adolescents [15-22]. US and European programs report rates of disclosure ranging from 17-75% [23-30]. Median ages of disclosure for children in US and European studies (7.5-10 years) are lower than in studies from Africa (8.7-15 years)[16, 23, 27-33]. Rates of disclosure in Africa remain low even in programs where the majority of children (73-85%) are receiving ART [16, 21, 32] Disclosure of HIV status requires that children comprehend information regarding the diagnosis and its implications. Thus, the age, cognitive development, and level of education of a child can significantly influence timing of disclosure [17, 21, 26-28, 32, 34].

Because pediatric HIV may result in neurocognitive impairments, emotional/cognitive maturity may be delayed therefore also delaying disclosure. In addition, caregivers are often reluctant to inform children of their HIV diagnosis because of concerns regarding inadvertent disclosure of the family's HIV status, perceptions of the child's inability to cope with results, and guilt regarding transmission [35-40]. Caregivers may have witnessed children lose friends and social standing when their status became known [41, 42]. Caregivers, who are often also infected with HIV, may have had difficulty when they learned their own HIV status, which then impacts their perception of the benefits of disclosure. Previous studies have demonstrated that the HIV serostatus of the caregiver is a key factor in disclosure [17, 28]. Among HIV positive caregivers, studies in Europe, South Africa, and Ethiopia observed that caregivers who had disclosed their own status were more likely to have also disclosed the child's status to the child [17, 19, 27].

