Approach: *We will randomize 20 clinics to receive the ATP or no intervention (SOC) and compare disclosure and appropriate transition using pre-specified milestones among a group of children and adolescents with heterogeneous ages. During early implementation, we will monitor fidelity to the intervention using modified plan-do-study-act (PDSA) cycles. We will track implementation outcomes and factors influencing implementation during the initial ATP implementation phase (6 months). During this time, the study team will discuss and support changes to refine the tool as needed at each facility. Following the initial implementation period, HCWs will take part in focus group discussions to share their suggestions for optimizing the transition tool based on their experience. Understanding personal experiences with the tool will provide an opportunity for lessons learned and continued refinement of the intervention. At the end of the study, we will qualitatively evaluate acceptability, appropriateness and feasibility of the ATP by conducting interviews and FGDs with all HCWs from implementing sites and adolescents from a sub-set of intervention sites, purposively selecting to include participants from high and low performing facilities. We will also conduct pre-trial and post-trial surveys with adolescents and HCWs to quantitatively assess acceptability, appropriateness, feasibility of the ATP and implementation intervention fidelity. At 6-monthly intervals, we will collect readiness assessment information from adolescents in participating clinics.*

SECTION 3: STUDY OUTCOMES

Aim 1

- Prevalence of transition
- Age at transition
- Co-factors for retention
- Age at disclosure
- Co-factors of disclosure
- Individual level co-factors of effective transition
- Facility level co-factors of effective transition

Aim 2

- Adapted transition tool

Aim 3

- The primary outcome is **disclosure** among non-disclosed adolescents and **effective transition and transition readiness** among disclosed adolescents

- Disclosure will be defined as no, partial or complete disclosure. Time to disclosure and age at disclosure will also be assessed.
- Effective transition with retention in care will be defined as completing a visit on the adult day or completing a visit without a caregiver and repeat visits continuing for at least 6 months after transition.
- Transition readiness will be defined as change in response to readiness assessment questions administered every 6 months

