- We assume that 100 of these eligible clients will be aged 6-15 and that the rate of complete disclosure will be 15% in the control clinics based on our prior studies and the literature with increased prevalence per year of age in this age-window.
- We assume that 100 of these eligible clients will be aged 15-24 years and that 20% (n=20) will be receiving care in a pediatric program and could be eligible to transition (200 per RCT arm). During 2-year follow-up, we anticipate that in the control arm 20% will transition and 10% will transition effectively.

With 10 intervention and 10 control sites, we will have sufficient power to detect an increase in proportion of adolescents with disclosure from 30% to 50%, an increase in proportion who initiate transition from 50% to >80%, and an increase in proportion with effective transition from 10% to 20%. This assumes alpha of 0.05, 80% power, and a conservative estimate of the coefficient of variation of 0.3 (Table 6). Heterogeneity between clusters is expected to decrease with control for baseline testing rates, leading to increased power beyond that which is noted above.

Table 8: Power and sample size ranges

	Outcome Control	Outcome Intervention	Number of clinics per RCT arm to detect difference
Age 10-15	N=1000 (100/clinic)	N=1000 (100/clinic)	
Disclosure process started (proportion)	50% 50% 50%	>80% >90% 100%	9 6 5
Disclosure complete (proportion)	30% 30% 30%	50% 70%	8 4 3
Disclosure age median	14 years old	12 years old	NA
24-month LTFU	20%	10%	7
Age 16-24	N=1000 (100/clinic)	N=1000 (100/clinic)	
Transition discussed (proportion)	20% 20% 50%	40% 60% 100%	6 3 5
Transition complete (proportion)	10%	20%	7
Transition satisfaction	50%	70%	NA
24-month LTFU	25%	15%	10

For the provider and adolescent IDIs, we will select healthcare providers and adolescents from ATP-implementing clinics for individual interviews. Clinics will be purposively selected from among all ATP-implementing clinics. We will purposively select clinics for interviews based on performance, including high and low performing sites as appropriate based on the outcome of the intervention. If the majority of clinics do well, we will purposively select a higher proportion of low performing clinics to understand why they had challenges. If the majority of the clinics do poorly, we will purposively select a higher proportion of high performing clinics to understand how they succeeded.

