Focus group discussions and interviews will be recorded and transcribed verbatim. Transcripts will be coded and thematic analysis will be conducted on the transcripts using ATLAS.ti. At least 2 researchers will independently code the data, coordinating their findings and analyses to create a comprehensive codebook and concept map. Themes related to how to culturally adapt and improve the described transition intervention, and how to improve clinical care for HIV-infected adolescents, will be identified and used to revise the implementation of the intervention.

Aim 3

The primary analysis will be an intent-to-treat (ITT) analysis.

We will use generalized estimating equations (GEE) clustered on facility level to compare differences in age-appropriate disclosure and change in transition readiness over time between control and intervention communities during baseline and intervention periods. In order to decrease variability between our sites and increase precision of our outcome measures, we will control for baseline adolescent disclosure and transition proportions in our models. We hypothesize that the increases in disclosure and transition proportions between the baseline and intervention periods will be greater among intervention than control facilities.

The first 6 months of the intervention will be considered a “catch up” period; while outcomes will be compared during the full study period, a sub-group analysis is planned for the first 6 months to see if the effect of the intervention is greater during the “catch-up” period.

Focus group discussions and interviews will be recorded and transcribed verbatim. Transcripts will be coded and thematic analysis will be conducted on the transcripts using ATLAS.ti. At least 2 researchers will independently code the data, coordinating their findings and analyses to create a comprehensive codebook and concept map. Themes related to implementation acceptability, feasibility, appropriateness and challenges and successes will be identified. Proportions satisfied with the transition and disclosure process will be compared between the 2 arms.

SECTION 12: ETHICS/PROTECTION OF STUDY PARTICIPANTS

COVID-19 ADAPTED STUDY PROCEDURES

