- c. Self-management readiness score
- d. Communication readiness score
- e. Support readiness score

Analysis

Primary analysis ITT: Mixed effects linear regression to compare transition readiness scores (overall and by domain) over time in control and intervention sites with adjustment for multiple testing (Benjamin-Hochberg method).

Time points: Enrollment, month 6, month 12

Sample size and power table

Assumptions: 80% power, alpha 0.05, ICC 0.2, average cluster size of 50

Mean difference	SD	Number of Clusters per Arm
0.5	1	4
0.5	2	15
1.0	2	4
1.0	3	9
1.5	3	4
1.5	4	7
2.0	5	6
2.0	6	9

Secondary outcomes

- a. Overall retention in 10-24 year olds: defined as proportion of 10-24 year olds completing visits within 6 months of last visit
- b. Overall viral suppression: defined as proportion of 10-24 year olds with viral load of less than 1000 copies per ml after at least 6 months of ART

Analysis

Overall retention/suppression: Generalized estimating equations (GEE) to compare retention and viral suppression in intervention and control sites

Time-points: Baseline, month 6, month 12

Minimum detectable differences in proportions with outcomes

Assumption: 80% power, alpha 0.05, ICC 0.2, 10 clusters per arm, average cluster size of 50

Proportion with outcome in arm 1	Proportion with outcome in arm 2
0.2	0.31
0.3	0.44
0.4	0.56

0.5	0.69
0.6	0.81
0.7	0.93

Exploratory analyses

1. Post-transition retention defined as completing and adult clinic visit day after transfer to adult services and at least 1 other visit within 6 months of the adult visit (total of 2 visits):
Analysis: GEE to compare post-transition retention in intervention and control sites
2. Principal components analysis to identify the most representative components of data in the 4 domains of the readiness assessment checklist (HIV treatment literacy (Q 1-5), self-management (Q6, 7, 9-14, communication Q16-19, support 20-22) and then factor analysis to determine the most important components.
3. Proportion of children with full disclosure and time to full disclosure. Children who do not know their HIV status from HCW assessment. Child will be asked why they are taking medicine; if they report they have HIV they have reached full disclosure. If they mention any other illness or other responses they will not have reached full disclosure.
End point: Child says they have HIV in response to the question “why are you taking your medicine”
Analysis: Descriptive %, time to full disclosure

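### The protocol says disclosure depends on age, but no Aim 3 model adjusts for the individual's age; adding it costs almost nothing and would bring a modest, assumption-dependent gain in precision

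*Combined protocol and SAP*

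**What the plan says.** Protocol 2b (Aim 3, Approach) says that the trial will "compare disclosure and appropriate transition using pre-specified milestones among a group of children and adolescents with heterogeneous ages". Protocol 1b states that "the age, cognitive development, and level of education of a child can significantly influence timing of disclosure". Protocol 11a assumes a control-arm disclosure rate "with increased prevalence per year of age in this age-window". Protocol 1b also cites programme data in which "15-24 year old youth had 2-fold higher loss to follow-up than younger adolescents".

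The models are these:

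- Protocol 11b, disclosure: a GEE clustered on facility, in which "we will control for baseline adolescent disclosure and transition proportions in our models". The outcome is labelled *age-appropriate* disclosure, but the label is not defined there or elsewhere.
- SAP, retention and viral suppression at ages 10-24: "Generalized estimating equations (GEE) to compare retention and viral suppression in intervention and control sites", at baseline, month 6 and month 12. No covariate is named.
- SAP, exploratory item 3, disclosure: percentages and time to full disclosure, described only.

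Restricted randomisation is optional (protocol 5e and 7c). The examples in 7c are location type and clinic size, not age. Date of birth is among the items listed for record abstraction in 7a. Section 3 makes age at disclosure an outcome, so age must be held for these participants.

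**The concern.** With ten clinics per arm, randomisation does not closely balance the age mix. If disclosure climbs with each year of age, a clinic with older undisclosed children will show more disclosure whichever arm it is in. An individual age term removes that part of the variation.

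The planned baseline proportion is only a partial substitute. Section 3 sets the disclosure outcome in adolescents who are undisclosed at the start, so none of them has an informative baseline value of their own. A clinic's baseline proportion can be high because its children are older or because its staff disclose more readily, and it does not describe the ages of those still undisclosed.

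At stake are the precision of the disclosure comparison and the credibility of any age adjustment. The trial is unmasked, so an age term added after an imbalance has been seen would look data-driven.

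**Working it through.** **1. Reproduce the plan's figure.** The trial is sized "to detect an increase in proportion of adolescents with disclosure from 30% to 50" per cent. The text adds: "This assumes alpha of 0.05, 80% power, and a conservative estimate of the coefficient of variation of 0.3". Table 8 gives 100 children per clinic. The unmatched cluster formula is

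c = 1 + (z₀.₉₇₅ + z₀.₈₀)² × [p₀(1−p₀)/m + p₁(1−p₁)/m + k²(p₀² + p₁²)] / (p₁−p₀)²

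With p₀ = 0.30, p₁ = 0.50, m = 100 and k = 0.3, the bracket is 0.0021 + 0.0025 + 0.09 × 0.34 = 0.0352. So c = 1 + 7.849 × 0.0352/0.04 = 7.91, which rounds up to the 8 in Table 8. With ten clinics per arm, √(9 × 0.04/0.0352) − 1.96 = 1.24, giving power of 89.2%. Because k covers all between-clinic variation, age mix is already inside this calculation.

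**2. How much of that variation could be age.** Neither the slope nor the spread of clinic mean age is given, so both are assumed: 3 to 10 percentage points per year, and an SD of 0.25 to 0.75 years. The age part of the between-clinic variance is (slope × SD)². Its share of the control-arm variance is that figure divided by (0.3 × 0.30)² = 0.0081. Removing it from both arms subtracts 2 × (slope × SD)² from 0.0352. The SD of the chance shift in the arm difference is slope × SD × √(2/10).

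| Slope (points/year) | SD of clinic mean age (years) | Share of variance | Clinics per arm | Power, 10 per arm | 95% range of chance shift (points) |
|---|---|---|---|---|---|
| 3 | 0.25 | 1% | 7.88 | 89.3% | ±0.7 |
| 5 | 0.5 | 8% | 7.66 | 90.3% | ±2.2 |
| 8 | 0.5 | 20% | 7.28 | 91.8% | ±3.5 |
| 10 | 0.75 | 69% | 5.70 | 97.2% | ±6.6 |

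For the second row, (0.05 × 0.5)² = 0.000625, and 0.000625/0.0081 = 8%. Then 1 + 7.849 × (0.0352 − 0.00125)/0.04 = 7.66. These rows assume no baseline adjustment, so they are upper bounds on what age adds to the planned model.

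**3. Allow for the planned baseline adjustment, at clinic level.** A simulation of 20 clinics with 100 children each used slopes of 3 to 8 points per year and age SDs of 0.25 to 0.75 years, with half of the other clinic variance stable over time. Adjusting for the baseline proportion cut the SE from about 0.043-0.046 to 0.033-0.039. Adding clinic *mean* age then changed it by only about −2% to +3%. This run used neither the undisclosed-only cohort nor individual age.

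**4. Individual age in the undisclosed-only cohort.** Assumed inputs: ten clinics per arm, 100 children per clinic, ages 6-15 or 10-15, log-odds slope 0.2 to 0.35 per year, SD of clinic mean age 0.4 to 0.8 years, clinic effect SD 0.35 logits, and correlation of clinic effects between baseline and follow-up of 0 to 0.8; 400 runs per setting. Age was entered with a quadratic.

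- On top of the baseline proportion, slope 0.35: SE 2% to 17% lower in all 12 settings.
- On top of the baseline proportion, slope 0.2: from 7% lower to about 1% higher.
- Age as the only covariate: SE 0% to 20% lower.

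A second simulation of the same cohort, also on assumed inputs, gave from 13% lower to 2% higher on top of the baseline proportion, mostly 0-5% lower. With age alone the SE was 0-15% lower. The small increases are within simulation noise.

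**5. What this is worth.** A 5% lower SE equals about 1/0.95² − 1 = 11% more clinics, roughly one extra per arm. At the favourable end, 17% equals 1/0.83² − 1 = 45%. The gain is largest when the age slope is steep and clinic practice unstable over time, and close to nil when the slope is shallow and practice stable. No figure was calculated for retention or viral suppression.

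**The case against.** The strongest reply is that the planned model already handles much of the age mix. Protocol 11b compares baseline with intervention periods and controls for baseline proportions, and step 3 shows that this captures most of a clinic's stable age difference. That stands, and it is why the typical gain is small. It does not remove the gain in the undisclosed-only cohort, where the clinic proportion says little about the ages of those at risk. The protocol is not entirely clear on that cohort: Section 3 points to undisclosed participants, while 11b speaks of increases in proportions between periods.

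The protocol also does not ignore age. It sizes separate age bands in Table 8, judges each participant within their own stage, and reports age at disclosure. But the bands are used for sizing, considerable age spread remains within each, and an undefined *age-appropriate* label is not an adjustment. Restricted randomisation could in principle include age, since its list is open, but it is optional and does not name it.

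The SAP further limits the consequence. Its summary and analysis text make disclosure exploratory and descriptive, although its Appendix 1 lists disclosure under a secondary heading and protocol Section 3 makes it primary. In-person disclosure activities were also suspended under the COVID-19 procedures. The SAP therefore has no between-arm disclosure test whose power could be improved. The point bears on the protocol's GEE, on the SAP's secondary GEE, and on any arm comparison of the exploratory percentages.

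**Conclusion.** The omission is real and worth correcting, but modest. Under the assumptions above, individual age on top of the baseline proportions changes the SE of the disclosure difference by between about nil and 13-17% lower, typically 0-5% lower. With no other covariate the reduction is about 0-20%. Every figure depends on an age slope and a clinic age spread that the documents do not give. For retention and viral suppression the argument is qualitative: the protocol cites an age gradient in loss to follow-up, and the SAP model has no covariate to absorb it.

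Three stronger readings are tempting, and the documents do not support them.

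- A reader might infer that the trial is undersized or its test invalid. It is not: age variation sits within the coefficient of variation of 0.3 and within a facility-clustered SE. Chance age imbalance is part of that same uncertainty, not a second fault.
- A reader might compare age-adjusted results with raw clinic proportions and find SE reductions of 5-24%, with power rising from 73-90% to 87-98%. That comparator leaves out the planned baseline adjustment, and the calculation sets 30% against about 44%, not the planned 30% against 50%.
- A reader might infer that the SAP's primary test is at risk. That test concerns transition readiness at ages 15-24, and none of these calculations bears on it.

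**What to change.** In protocol 11b, add the individual's age at baseline as a prespecified covariate in the facility-clustered GEE for disclosure, alongside the baseline proportions and not in place of them. Define *age-appropriate* disclosure or drop the term. In the SAP, add the same age term to the GEE for retention and viral suppression. If the exploratory disclosure percentages are to be compared between arms, state that the same age-adjusted, facility-clustered model will be used, and report a standardised risk difference so that the effect stays marginal. A quadratic term in age is optional.

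The cost is a few lines of wording and one variable already abstracted. An individual-level covariate uses essentially no clinic-level degrees of freedom, and the simulations showed no loss beyond noise. The wording should be fixed before outcomes are compared by arm.
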